#### **5.3.5. Safety Endpoints**

Missing safety data will be handled according to Pfizer standards.

#### **5.3.6. Other Variables**

For a patient without an available Ph status data at screening, cytogenetics data of the patient at Month 3 will be impute as the Ph status at screening only if a study monitor is able to confirm the Ph status before screening and records it in an appropriate document such as a monitoring record.

Other variables except for endpoints described in [Section 5.3](#) will not be imputed.

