- p. Bone marrow obtained as part of standard of care prior to signing informed consent document can be used at screening as long as it was collected within 28 days prior to registration. **Once CCyR or MMR has been achieved, bone marrow aspirates will be performed only if clinically indicated (eg, suboptimal response, suspect disease progression or failed/inadequate Week 48 assessment).** Patients completing treatment for cytogenetically confirmed treatment failure do not need to repeat bone marrow at treatment completion. Patients ending treatment for reasons other than cytogenetically confirmed treatment failure must undergo treatment completion bone marrow aspirate if previous bone marrow aspirate performed >12 weeks prior. If loss of major molecular response occurs in combination with a $5 \times$ PCR increase for BCR-ABL, a bone marrow aspirate for chromosome banding analysis (CBA) should be obtained.
- q. Cytogenetics analysis must be performed so that dose-escalation rules can be appropriately applied (eg, patient should not have 12-week bone marrow aspirate before Day 84 so that at least 12 weeks from first dose is assessed). Cytogenetic assessment of bone marrow aspirate will be performed locally. If cytogenetics is used, it must be performed by CBA of marrow cell metaphases, counting at least 20 metaphases, at 12, 24, 36, and 48 weeks, until CCyR or MMR is achieved, then every 48 weeks.
- r. Local PCR result for BCR-ABL confirmation is acceptable prior to informed consent where this has already been conducted as part of initial diagnosis of a patient, provided this molecular diagnosis of CP CML has been made ≤ 6 months prior to registration. However, central PCR sample must always be conducted after informed consent, as this is a study-specific procedure.

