7.1. Efficacy Assessment

7.1.1. Efficacy Assessment Methods

Efficacy will be determined by physical examination, analysis of peripheral blood and bone marrow. Automated CBC (eg, hemoglobin, red blood cell (RBC), WBC, platelets, and hematocrit), differential counts (eg, neutrophils, basophils, eosinophils, lymphocytes, metamyelocytes, myelocytes, monocytes, promyelocytes, myeloblasts, unspecified blast cells and band cells), bone marrow differential (eg, plasma cells, promyelocytes, myelocytes, metamyelocytes, eosinophils, lymphocytes, monocytes, myeloblasts, erythroblast, basophil, neutrophils, band neutrophils, unspecified blast cells, megakaryocytes, and erythroid precursors), molecular analysis for BCR-ABL transcripts, cytogenetics, physical examination, and mortality will be used to determine the response to treatment as described in [Appendix 2](#). Molecular and hematologic response rates will be assessed for all patients. Cytogenetic response will be assessed in all Ph+ CML patients. The timing of these assessments is presented in the [SCHEDULE OF ACTIVITIES](#) table.

Molecular response monitoring using RT-qPCR for BCR-ABL copy number will be performed on peripheral blood on all patients harboring b2a2 and/or b3a2 transcripts and will be sent to a central vendor for performance and assessment on the IS; sample collection for molecular response monitoring is described in Section [7.1.1.1](#).

Differential count and cytogenetic assessment on bone marrow aspirate will be performed locally.

Bone marrow obtained as part of standard of care prior to signing the informed consent document may be used at screening as long as it was collected within 28 days prior to registration. Patients completing treatment for cytogenetically confirmed treatment failure do not need to repeat bone marrow at treatment completion. Patients ending treatment for reasons other than cytogenetically confirmed treatment failure must undergo treatment completion bone marrow aspirate if the previous bone marrow aspirate was performed >12 weeks prior to treatment failure. Additional bone marrow aspirations and cytogenetics will be done as indicated (eg, suspect disease progression or failed/inadequate Week 48

[Month 12] assessment). If confirmed loss of MMR occurs in combination with a $5 \times$ PCR increase for BCR-ABL, a bone marrow aspirate for cytogenetics should be obtained.

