### 3.2.2. CCyR

The CCyR by 12-month visit will be assessed.

The CCyR is defined as absence of detectable Ph. See [Appendix 1.2](#) for the details.

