#### **4. ANALYSIS SETS**

Data for all patients will be assessed to determine if patients meet the criteria for inclusion in each analysis population prior to releasing the database and classifications will be documented per standard operating procedures.

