##### **4.2. Modified as-Treated Population**

The modified as-treated population will consist of all enrolled patients with Ph+ CP CML harboring b2a2 and/or b3a2 transcripts who received at least 1 dose of study drug.

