## **6.1. Primary Endpoint**

### **6.1.1. MMR at 12 Months**

#### **6.1.1.1. Primary Efficacy Analysis**

The MMR at 12 months (48 week) will be analyzed using the hypothesis test of a one-sample binomial proportion test with the normal approximation (also refer to [Section 5.1](#)). The two-sided 90% CI of MMR rate at 12 months (48 weeks) will also be calculated.

The MMR at 12 months (48 weeks) is counted only if the response is demonstrated at the 12-month (48-week) visit; any MMR gained and lost before the 12-month (48-week) visit is deemed a non-response as is the case where the MMR is never achieved at or before 12 months (48 weeks).

The modified as-treated population will be used in the primary efficacy analysis.

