### **6.5.1. Baseline Summaries**

Baseline variables including the body weight and Ph status at the screening period will be summarized descriptively for both the modified as-treated population and the as-treated population according to [Section 5.2.1](#) and [Section 5.2.2.](#), respectively. The body mass index will be derived using the height and body weight at the screening period and will be reported as a baseline variable.

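### SAP 5.3.6 fills a missing screening Ph status with the Month 3 on-treatment result instead of the confirmed pre-treatment status, so a responding Ph+ patient could be recorded as Ph-

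*SAP*

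**What the plan says.** SAP section 5.3.6 covers a patient with no Ph result at screening. Cytogenetics from "Month 3 will be impute as the Ph status at screening only if a study monitor is able to confirm the Ph status before screening". The monitor must also record that confirmation in a suitable document. The SAP version history says only that an imputation method was being supplied.

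Four other places bear on how this works:

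- **Timing.** Footnote q of the protocol's Schedule of Activities says a "patient should not have 12-week bone marrow aspirate before Day 84 so that at least 12 weeks from first dose is assessed". The Month 3 marrow is therefore always an on-treatment sample.
- **Meaning of zero Ph+ cells.** SAP section 3.2.2: "The CCyR is defined as absence of detectable Ph". SAP Appendix 1.2 puts a complete response at 0% Ph+ cells.
- **Stated use of the screening value.** SAP section 6.5.1: "Baseline variables including the body weight and Ph status at the screening period will be summarized descriptively".
- **Population.** SAP section 4.2 defines the modified as-treated set as "all enrolled patients with Ph+ CP CML harboring b2a2 and/or b3a2 transcripts who received at least 1 dose of study drug". SAP section 6.1.1.1 adds: "The modified as-treated population will be used in the primary efficacy analysis". SAP section 6 restricts analyses of cytogenetic data to the same set.

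**The concern.** Ph status at screening is a pre-treatment fact. The rule fills it with a measurement that the drug is meant to change. At Month 3 a Ph+ patient in CCyR and a Ph- patient give the same result, so the imputed value cannot tell them apart.

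The condition does not cure this. The rule operates only when the pre-treatment status has been confirmed, and protocol section 4.1 bars patients already known to be Ph-. The confirmed status should therefore be Ph+. The Month 3 value can then only repeat what is known or wrongly contradict it, and neither document says which source prevails.

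The baseline description of Ph status is at stake directly. If the analysis programs take the same variable to decide who is Ph+ for the modified as-treated set, entry to the primary analysis would also depend on an on-treatment response.

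**Working it through.** **Step 1: follow the rule for one patient.** Take a patient with no screening cytogenetics and a monitor-confirmed Ph+ status.

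| Month 3 marrow | Screening value under 5.3.6 | Agrees with the confirmed status? |
|---|---|---|
| At least one Ph+ metaphase | Ph+ | Yes |
| No Ph+ metaphase (CCyR) | Ph-, if read literally | No |

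SAP section 6.2.2 rounds the percentage of Ph+ cells upward, so only a count of zero gives 0%. One Ph+ cell in 20 metaphases gives 5%. The error therefore runs one way: it affects complete cytogenetic responders only.

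**Step 2: reproduce the plan's figures.** Inputs from SAP section 5.1 are null rate 25%, alternative 40%, n=60 and one-sided alpha 5%.

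- Critical count: 60×0.25 + 1.645×√(60×0.25×0.75) = 15 + 5.52 = 20.52, so 21 responders, as stated.
- Power: Φ[(0.15 − 1.645×√(0.1875/60)) / √(0.24/60)] = Φ(0.918) = 0.821. This agrees with the 82.1% in protocol section 9.1.

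**Step 3: effect on the primary test, if the imputed variable assigned the population.** Suppose k patients in CCyR at Month 3, all in MMR at Week 48, were coded Ph- and left the set. Numerator and denominator both fall by k. The statistic is z = (x/n − 0.25)/√(0.1875/n), with a one-sided p-value. The documents do not give k; 0 to 3 is an assumption.

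| Full set (k=0) | k=1 | k=2 | k=3 |
|---|---|---|---|
| 21/60, p=0.037 | 20/59, p=0.057 | 19/58, p=0.086 | 18/57, p=0.126 |
| 22/60, p=0.018 | 21/59, p=0.030 | 20/58, p=0.048 | 19/57, p=0.073 |
| 23/60, p=0.009 | 22/59, p=0.015 | 21/58, p=0.024 | 20/57, p=0.039 |
| 24/60, p=0.004 | 23/59, p=0.007 | 22/58, p=0.012 | 21/57, p=0.020 |

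Losing one or two responders reverses the decision only at 21/60. Losing three does so at 21/60 and 22/60. At the design rate (24/60), success survives the loss of four (20/56, p=0.032).

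**Step 4: how likely the critical total is.** At a true rate of 40%, the exact chance of at least 20 responders in 60 is 0.8830, and of at least 21 is 0.8214. Hence P(20) = 0.0616 and P(21) = 0.0616 × (40/21) × (0.40/0.60) = 0.078. This is the chance of landing on the one total at which a single lost responder matters, before allowing for whether any such loss occurs.

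**The case against.** The strongest reply is that the condition was meant as a safeguard: Month 3 data are accepted only when a pre-treatment source establishes the Ph status. On that view nobody would code a documented Ph+ patient as Ph- because of a later response. The authors may well have intended this, but the sentence makes Month 3 the value and the confirmation the gate, and gives no order of precedence.

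A reader might infer that the SAP removes early responders from the primary analysis. The documents do not say so. Section 4.2 requires Ph+ disease and does not name the screening variable. A patient with confirmed Ph+ status meets that definition whatever stands in the baseline field. Under SAP section 4, patients are also "assessed to determine if patients meet the criteria for inclusion in each analysis population prior to releasing the database". That review could expose a conflict, although the SAP gives no rule for settling it.

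A reader might also infer that the MMR rate could rise, through confirmed patients who have no Month 3 sample and are dropped as non-responders. That does not follow either. Section 5.3.6 does not class such a patient as Ph-, and section 4.2 would still admit a confirmed Ph+ patient.

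Three further points for the plan stand:

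- The group is narrow. Marrow is scheduled at screening, and protocol section 7.1.1 adds: "Bone marrow obtained as part of standard of care prior to signing the informed consent document may be used at screening", within a 28-day limit before registration.
- Dropping responders is conservative for efficacy.
- The Week 48 MMR analysis in the as-treated population (SAP section 6.3.1) keeps everyone. SAP section 6 lets as-treated analyses be omitted only when the two populations are identical, so it would appear whenever a treated patient was excluded. It carries no hypothesis test (SAP section 5.1).

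**Conclusion.** The rule as written is faulty, and the matter is minor. For any confirmed Ph+ patient without screening cytogenetics who is in CCyR at Month 3, a literal application gives a wrong baseline Ph value. That follows from the text alone.

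Any effect on the primary MMR test or the CCyR analyses rests on an assumption that the SAP does not make: that the imputed field also assigns the modified as-treated set. Granting it, the effect lowers the observed MMR rate when the patients lost are Week 48 responders. With an assumed loss of up to three such patients, the decision changes only at 21 or 22 responders of 60. The number of patients without a screening Ph result is not given and is probably small.

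**What to change.** Replace the first sentence of SAP section 5.3.6 with:

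> For a patient without screening cytogenetics, the documented pre-treatment Ph status confirmed by the monitor is used as the Ph status at screening, whether or not a Month 3 result exists. Absence of Ph+ cells on treatment does not classify a patient as Ph-.

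Nothing is lost for patients whose earlier status cannot be confirmed, because the present rule gives them no value either. The population definition stays as it is. No extra analysis is needed, since the as-treated Week 48 analysis already includes these patients.

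The cost is two sentences in place of one and a small data step. The confirmed status may now sit only in a document such as a monitoring record, so it must be carried into the analysis data for the few patients concerned.

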## **6. ANALYSES AND SUMMARIES**

All efficacy analyses will be performed using the modified as-treated population unless otherwise specified. In case the as-treated population is completely the same as the modified as-treated population, analyses for efficacy endpoints using the as-treated population may be omitted.

Patients without the b2a2 or b3a2 transcript will be counted as non-responders of MMR in the as-treated population. Analyses including cytogenetic data will only be performed on the modified as-treated population as Ph- patients are not assessable for cytogenetic response.

## **6.1. Primary Endpoint**

### **6.1.1. MMR at 12 Months**

#### **6.1.1.1. Primary Efficacy Analysis**

The MMR at 12 months (48 week) will be analyzed using the hypothesis test of a one-sample binomial proportion test with the normal approximation (also refer to [Section 5.1](#)). The two-sided 90% CI of MMR rate at 12 months (48 weeks) will also be calculated.

The MMR at 12 months (48 weeks) is counted only if the response is demonstrated at the 12-month (48-week) visit; any MMR gained and lost before the 12-month (48-week) visit is deemed a non-response as is the case where the MMR is never achieved at or before 12 months (48 weeks).

The modified as-treated population will be used in the primary efficacy analysis.

## **6.2. Secondary Endpoints**

### **6.2.1. MMR by 12 and 18 Months**

Evaluations of MMR by 12 and 18 months will be assessed using the frequency tables, respectively. The two-sided 90% CI will also be calculated. For the analysis of MMR by 12 and 18 months, a patient is counted as a responder if the MMR occurs at or before 12 and 18 months, respectively, even if the MMR is subsequently lost at or before the 12-month and 18-month time point, respectively. A patient never achieving the MMR at or before 12 and 18 months will be considered a non-responder, respectively.

The MMR by 18 months will only be summarized at the final analysis (FA; refer to [Section 7.2.3](#) with respect to the FA).

#### **6.2.2. CCyR**

Evaluations of CCyR by 12 months (48 weeks) will be assessed using the frequency tables. The two-sided 90% CI will also be calculated. The CCyR rate by 12 months is defined as the proportion of patients demonstrating CCyR at or before 12 months (48 weeks). The percentage of Ph+ cells will be calculated according to the following formula:

$$\text{ceil}(100 \times \text{the number of Ph+ cells} / \text{the number of metaphases}),$$

where ceil() denotes a ceiling function.

The proportion of patients who have confirmed loss of CCyR will also be evaluated.

#### **6.2.3. Duration of Response**

The duration of MMR and CCyR will be based on the estimations of the quartiles of duration and yearly rates using the Kaplan-Meier method.

For the analysis of MMR and CCyR, the proportion of patients who have confirmed loss of response will also be evaluated, respectively.

The duration of MMR will be analyzed for MMR responders in the modified as-treated population and those in as-treated population separately. The duration of CCyR will be analyzed for CCyR responders in the modified as-treated population.

#### **6.2.4. EFS**

EFS will be analyzed using the cumulative incidence method adjusting for the competing risk of treatment discontinuation without the event, and yearly rates and percentiles will be displayed. This will be indicated as the on-treatment EFS. As a definition of “on-treatment” is described in [Section 6.3.5](#), the transformation to AP and BP on treatment will be considered as an event in the analysis of EFS. This means that if the first transformation to AP and BP is occurred after 28 days from the last dose, this will not be considered as an event in the analysis of EFS.

As a reference, the EFS using the transformation to AP and BP occurred after 28 days from the last dose instead of the transformation to AP and BP on treatment will also be assessed using the same analysis method. This will be indicated as the off-treatment EFS.

The on-treatment EFS and off-treatment EFS will be analyzed in the modified as-treated population.

The off-treatment EFS will only be evaluated at the FA (refer to [Section 7.2.3](#) with respect to the FA).

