- Cumulative CHR in patients with Ph+ and both Ph+ and Ph- CP CML.
- Time to transformation to AP and BP CML on treatment.
- Type of mutations present at treatment completion/discontinuation or suboptimal response.
- Potential results from exploratory analyses of banked biospecimen (these results may or may not be generated in the context of the present study).

Study Design

Study Overview

This is a Phase 2, open-label, single-arm study designed to evaluate efficacy and safety of bosutinib alone in Japanese adult patients with newly diagnosed CP CML. The primary

endpoint is MMR at 12 months in newly diagnosed Japanese Ph+ CP CML patients harboring b2a2 and/or b3a2 transcripts. Patients will receive bosutinib treatment at a starting dose of 400 mg QD. The dose of bosutinib is allowed to be escalated (up to a maximum of 600 mg QD) for unsatisfactory response or reduced for toxicity.

This study has approximately 52 weeks of planned patient accrual. Each patient will have 12 months (48 weeks) of Core Treatment Phase and the following ≥ 24 months (96 weeks) of Extension Phase. After treatment discontinuation, the patient enters Long-Term Follow-Up. The Extension Phase or Long-Term Follow-Up will continue until the end of the study.

The study will be open for enrollment until approximately 60 Ph+ CML patients harboring b2a2 and/or b3a2 transcripts have been registered. Bone marrow aspirate to assess the Ph status will be obtained at screening, patients with known Ph- prior to registration are not eligible for this study. However, as confirmation of the Ph status prior to registration is not mandatory, Ph- CML patients may also be included. Approximately 3 Ph- CML patients are expected to be registered as approximately 5% of the patients with BCR-ABL-positive CML are diagnosed as Ph- CML.^{2,3} All patients will be treated and/or followed up to approximately 3 years (144 weeks) after registration of the last patient, or until study termination, whichever comes first. Patients who permanently discontinue study treatment will be followed for survival, investigator-assessed transformation to AP/BP, duration of response and disease progression, and initiation/response to further anti-cancer therapies, including stem cell transplantation (where applicable).

Study Treatments

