- v. All concomitant medications and non-drug supportive interventions will be recorded in the CRF from 28 days prior to registration and up to 28 days after the last dose of study treatment.
- w. The pre-dose PK samples should be collected before (within 3 hrs of) study drug administration on Days 1, 28, 56, and 84. 3 mL of whole blood for plasma drawn into a tube containing potassium ethylenediaminetetraacetic acid (EDTA). See Section 7.3. On PK sampling days, the bosutinib dose should be taken in the hospital under the supervision of the study site personnel. The bosutinib dose should be administered after the PK sample has been collected.
- x. Blood sample will be collected for bio-banking if specifically allowed by local Institutional Review Board (IRB) or EC; 1 tube of whole blood (prep D1) will be collected at Screening. If not collected on the designated collection day, collect at the next available time point when bio-specimens are being collected in conjunction with a patient visit.
- y. For patients remaining on treatment in the Extension Phase, the investigator should continue to perform biochemistry and hematology testing, per standard of care for CML patients and as clinically indicated in line with local guidelines including cytogenetics when indicated by bone marrow analysis. Patients will have mandatory AE and SAE collection follow-up. These are expected to take place at least every 12 weeks.
- z. Long-Term Follow-Up information will be collected via telephone contact up to approximately 3 years after registration of the last patient, or until study termination, whichever comes first, where possible for patients who discontinue the study early. Follow-up calls should be conducted every 12 weeks in the first two years, and then every 24 weeks. The timing of follow-up calls is calculated with Day 1 designated as the starting point.

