#### **5.3.4. Time-to-Event Data**

The primary missing data handling method will be censoring. A patient withdrawing from the study without experiencing the event of interest will be censored at the last valid (ie, evaluable) assessment of that event. A patient who fails on treatment, after missing two or more assessments of both hematologic and cytogenetic response, will be censored for on-treatment EFS at the last hematologic or cytogenetic assessment. A patient, who dies after treatment discontinuation during long-term follow-up and after missing two or more long-term follow-up assessments, will be censored for off-treatment EFS at the last assessment at which the patient was found to be alive and event-free. See also [Section 3.2.3](#) for duration of MMR or CCyR.

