#### **6.3.5. Time to Transformation to AP and BP CML**

The analysis of the time to transformation to AP and BP CML will be similar to that of the time to response described above.

The time to transformation to AP and BP CML is defined as the time from first dose to the first date of transformation to AP or BP CML. The transformation to AP and BP will be counted while a patient is on treatment up to 28 days after last dose. In the analysis of cumulative incidence (see [Section 5.2.3](#)), the competing risk is defined as treatment discontinuation without transformation. If transformation has not occurred, the patient will be censored at the last valid hematologic assessment.

Investigators should assess transformation to AP/BP according to the original definition of AP/BP CML (see [Appendix 1.3](#)). In a statistical analysis, some restrictions (see table footnotes in [Appendix 1.3](#)) are adopted in addition to the original definition.

Time to transformation to AP and BP CML will be analyzed for the modified as-treated population and as-treated population separately.

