#### **7.2.3. Final Analysis**

The FA will be conducted after releasing the study database. The endpoints described below will be reported at the FA.

- MMR by 18 months;
- Duration of MMR and CCyR;
- EFS (both on-treatment and off-treatment);
- OS;
- MMR at 18 months;
- Time to MMR, MR4.0, MR4.5 and CCyR;
- Time to transformation to AP and BP CML on treatment;
- Type of mutations present at treatment completion/discontinuation or suboptimal response;
- All safety endpoints.

No statistical hypothesis test will be planned at the FA.

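### Two event-free survival rules in the SAP are wrong as written: off-treatment EFS captures essentially no transformations, and item 4 excludes CCyR losses tied to CML-related discontinuation

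*SAP*

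**What the plan says.** **Off-treatment EFS.** SAP 6.2.4 analyses EFS by cumulative incidence, "adjusting for the competing risk of treatment discontinuation without the event". On-treatment EFS takes its window from SAP 6.3.5: "The transformation to AP and BP will be counted while a patient is on treatment up to 28 days after last dose". The section then adds a reference analysis, reported only at the final analysis: "the EFS using the transformation to AP and BP occurred after 28 days from the last dose instead of" the on-treatment transformation, which "will also be assessed using the same analysis method". It names no other competing risk and gives no separate follow-up rule. SAP 5.3.4 does give one. A patient who dies in long-term follow-up after missing at least two follow-up assessments "will be censored for off-treatment EFS at the last assessment at which the patient was found to be alive and event-free". In the protocol (Protocol Summary and Section 3), patients who stop treatment for good are "followed for survival, investigator-assessed transformation to AP/BP, duration of response and disease progression". Footnote z of the Schedule of Activities adds: "Long-Term Follow-Up information will be collected via telephone contact".

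**Loss of CCyR.** Protocol 9.2.2.4 requires at least one Ph+ metaphase, found again 4 or more weeks later, and places an exception for CML-related discontinuation right after that repeat requirement. SAP 3.2.4 item 3 places it likewise for loss of CHR. Item 4 places it right after the event name, with a pointer to SAP 3.2.3 for the definition. The version history says the condition was added in version 4 for consistency with the protocol.

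At the final analysis, "No statistical hypothesis test will be planned at the FA".

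**The concern.** An analysis labelled off-treatment should show what happens after patients stop the drug. Here the method inherited from on-treatment EFS closes each patient's record at the stop, which comes before the events the analysis is meant to collect. The substitution wording also takes out the transformations that on-treatment EFS does count. The reference analysis therefore cannot reveal late transformations, and it may show fewer events than the analysis it supplements.

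The second rule matters more, because EFS is a secondary endpoint. A CCyR loss serious enough to end treatment for CML is a clear EFS failure. If item 4 is programmed as it reads, that patient has no event unless item 2 (transformation) or item 3 (loss of CHR) is also met, and EFS looks better than under the protocol's definition.

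**Working it through.** The documents state no figure for EFS, so there is none to reproduce. The check is one of event order, counts and wording.

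**1. Order of events.** Let L be the date of last dose, D the date assigned to discontinuation, and T the date of an off-treatment transformation.
- By definition, T > L + 28 days.
- If D = L, then D < T. If D = L + 28, so as to respect the on-treatment window, then again D < T.
- In a first-event analysis the competing event at D comes first, and T is not counted.
- Exception: a dose hold longer than 28 days with formal discontinuation only after T. Protocol 6.5 allows holds beyond 4 weeks when the investigator and sponsor agree.
- A transformation at or before L + 28 is removed by the substitution wording.

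**2. Conflict with SAP 5.3.4.** Its rule for deaths in long-term follow-up after missed assessments needs patients to be at risk after D. If D had already ended their follow-up, the rule would have nothing to act on.

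**3. Size per event.** One event adds S(t−)/Y(t) to the cumulative incidence, where S is the proportion still free of both event and competing event and Y is the number at risk.
- No earlier censoring, 60 patients: S = Y/60, so the step is 1/60 = 1.67 points.
- With earlier censoring the step is larger. If half of those still at risk were censored beforehand (an assumption), it is 2/60 = 3.3 points. Earlier censoring is plausible, because SAP 3.2.4 censors at the earlier of the last hematologic or cytogenetic assessment.

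**4. Illustration with assumed counts, not estimates.** Of 60 patients, 3 have on-treatment events other than transformation, and 1 has an on-treatment transformation that meets no other item. Twelve discontinue without an event, and of these 1 later transforms and 1 later dies. There is no censoring before week 144.

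| Analysis | Events | Cumulative incidence |
|---|---|---|
| On-treatment EFS | 3 + 1 = 4 | 4/60 = 6.7% |
| Off-treatment EFS as written | 3 | 3/60 = 5.0% |
| Off-treatment EFS as repaired | 3 + 1 + 1 + 1 = 6 | 6/60 = 10.0% |

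The gap between the last two rows has three parts of 1/60 each: the restored on-treatment transformation, the off-treatment transformation and the follow-up death. The missing off-treatment transformation accounts for 1.7 points.

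**5. Scale.** In the earlier first-line study (protocol 1.2.3, 500 mg start), 2% of bosutinib patients progressed to AP or BP. That is 0.02 × 60 = 1.2 patients; the split between on and off treatment is not given. A simulation assumed discontinuation rates of 5 to 20% per year, transformation rates of 1 to 5% per year and 3 years of follow-up. Per 60 patients it gave about 0.1 to 1.9 off-treatment transformations and 1.3 to 7.8 on-treatment ones. With no dose holds in the model, the first-event rule counted none of the off-treatment ones under either dating of D.

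**6. Item 4, passages side by side.** Take a patient in CCyR in whom a Ph+ metaphase appears and whose treatment is then stopped for suboptimal response, before a second marrow.
- Protocol 9.2.2.4: an EFS event, with the repeat finding waived (taking suboptimal response as CML-related).
- SAP 3.2.3: a loss event for duration of CCyR, since an unconfirmed loss followed by such a stop counts as confirmed. Stopping for progressive disease also confirms a loss.
- SAP 3.2.4 item 4, read literally: no EFS event. The patient becomes a discontinuation without the event, which is the competing event.

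The literal exclusion also catches a loss that was confirmed before treatment was stopped for CML. Protocol 6.5 lists CCyR loss among the treatment-failure reasons for withdrawal, so such patients are foreseen.

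**The case against.** On the first rule, the competing risk is discontinuation without the event. Once the event is redefined, a patient who transforms later arguably did not discontinue without it, and SAP 5.3.4 suggests that this is the intent. The intent stands. The text does not: 6.2.4 imports the on-treatment method unchanged and nowhere lets a later transformation override an earlier stop. Even on that reading, on-treatment transformations remain dropped.

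It can also be said that a strict first-event rule with discontinuation dated at last dose would defeat the 28-day window of SAP 6.3.5. That is fair, since the SAP gives no dating rule. Dating the stop 28 days later rescues the window but not off-treatment EFS.

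On item 4, the cross-reference to 3.2.3, the parallel wording of item 3, the protocol and the version history all point to the intended meaning. So the intent is recoverable. A programmer still cannot assume that the protocol prevails, because protocol Section 9 and SAP Section 2 let the SAP modify the protocol's plans, with an amendment needed only for major changes to the primary endpoint.

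Three stronger readings are tempting and not supported:
- A reader might infer that the off-treatment count is zero in every circumstance. That needs the first-event reading and ignores long dose holds.
- A reader might take 5.0% against 10.0% as the size of the defect. Those counts are assumed, and the contrast combines three changes.
- A reader might infer that CHR and CCyR are not followed after discontinuation. The protocol says duration of response is followed, so the documents leave open which data would be usable.

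**Conclusion.** Both rules are wrong as written and should be corrected. Under a standard first-event analysis, off-treatment EFS counts essentially no off-treatment transformation, drops the on-treatment ones, and contradicts SAP 5.3.4. Item 4 states a different rule from the protocol's and, if programmed literally, understates events in a secondary endpoint.

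Each omitted event is worth at least about 1.7 percentage points with 60 patients, and more if others are censored earlier. The documents give no basis for the number of such events. The consequence is limited: off-treatment EFS is a reference analysis at the final analysis only, EFS carries no hypothesis test, and the primary endpoint is untouched.

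**What to change.** **SAP 6.2.4.** For off-treatment EFS, state that discontinuation is not a competing event, and change *instead of* to *in addition to*. Count on-treatment EFS events plus deaths and investigator-assessed transformations in long-term follow-up, with the SAP 5.3.4 censoring. Death is itself an event, so no competing risk remains and one minus the Kaplan-Meier estimate gives the cumulative incidence. State which off-treatment CHR and CCyR data, if any, are used, given that the protocol follows duration of response after discontinuation.

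**SAP 3.2.4 item 4.** Suggested text: *Loss of CCyR (see Section 3.2.3), with a second determination at least 4 weeks later; this confirmation is not required where treatment is discontinued for a CML-related reason.* State how CML-related maps to the progressive-disease and suboptimal-response reasons in 3.2.3.

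**Cost.** SAP wording and programming only. Survival and investigator-assessed transformation are already followed after discontinuation, so no new data are needed. Item 4 should be settled before on-treatment EFS is programmed for any analysis, and the 6.2.4 change before the final analysis.
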